# 9.6.1. Confirmed Objective Response Rate

The primary efficacy endpoint for the Phase 2 portion of the study is the confirmed ORR based on RECIST v1.1 as determined by BICR.

The confirmed ORR is defined as the proportion of subjects in the analysis set who have confirmed best overall response (BOR) as CR or PR. The confirmed ORR will be calculated as the number of subjects with a confirmed CR or PR divided by the number of subjects in the analysis population [ORR = (confirmed CR + confirmed PR)/# subjects] in each treatment group for the ITT Analysis Set.

ORR will be analyzed using a 2-sided Cochran-Mantel-Haenszel test stratified by stage and PD-L1 expression to compare the 2 treatment arms. Associated odds ratio and 95% CI will also be calculated. Additionally, ORR and the 95% exact CIs will be calculated using the Clopper-Pearson method for each of the 2 treatment arms. The secondary endpoint DCR and the 95% Clopper-Pearson CIs will be summarized as well.

The BOR is defined as the best response designation based on RECIST v1.1 as determined by BICR. Subjects who discontinue due to death due to disease progression, or disease progression, prior to having a post-Baseline tumor assessment will be classified as having a best response of PD. Subjects who discontinue prior to having a post-Baseline scan for other reasons will be counted as non-responders in the ITT analyses.

Objective response rate based on RECIST v1.1 as determined by BICR will be evaluated as a secondary endpoint in the Phase 3 portion of the study. Objective response rate per RECIST v1.1 and iORR per iRECIST by Investigator assessment will also be summarized.

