Per Sponsor's decision, site activation and study enrollment were terminated early for any subjects who had not signed informed consent yet, and the trial has been changed to an exploratory Phase 2 study. Additionally, it has been decided that there would not be in-house blinding, hence the sponsor analysis and reporting team would be unblinded to the assignment of subject treatment. Consequently, the SAP will not necessarily be consistent with the protocol. In case of any discrepancies, this SAP will govern the analysis of data from this study.

II. Study Design

A. Design Overview

This is a randomized, open-label, active-control, exploratory Phase 2 study of first-line CMP-001 administered by intratumoral (IT) injection in combination with intravenous (IV) nivolumab versus nivolumab monotherapy in subjects with Stage III or IV unresectable or metastatic melanoma who have not been previously treated with a programmed cell death protein 1 (PD-1) blocking antibody for metastatic disease. Subjects will be randomized in a 1:1 manner to Arm A to receive CMP-001 IT in combination with nivolumab IV or Arm B to receive nivolumab monotherapy according to the Schedule of Assessments (Protocol Table 1) and Protocol Section 5.1.

During the randomization process, treatment groups will be stratified based on: TNM Stage American Joint Committee on Cancer (AJCC) Cancer Staging Manual Eight Edition (M0/M1a/M1b vs. M1c/M1d), and tumor PD-L1 expression (>=5% vs. <5%).

The primary endpoint of ORR per RECIST v1.1 as determined by BICR will be assessed approximately by two disease assessments after the enrollment of the last subject and the end of the study after a maximum duration of 2 years of study treatment. Subjects enrolled may remain in the study and continue to receive study treatment until a reason for treatment discontinuation is reached but no further subjects will be enrolled from 24Jun2022.

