Note: 100DFU = 100-Day Follow-up; EOT = End of Treatment; LTSFU = Long-Term Survival Follow-up; IT = intratumoral; IV = intravenous; PTFU = Post-treatment Follow-up; Q3W = every 3 weeks; Q6W = every 6 weeks; Q12W = every 12 weeks; QW = weekly; W1D1 = Week 1 Day 1; W10D1 = Week 10 Day 1.

- a. The first CMP-001 dose (W1D1) may be administered subcutaneously or by IT injection at the discretion of the Investigator.
- b. Disease assessments performed predose beginning at W10D1 (-7 days) and repeated Q6W on treatment and then Q12W for subjects on treatment more than 1 year.

B. Study Population

See Protocol Sections 4.1 and 4.2 for a complete list of the inclusion/exclusion criteria.

C. Sample Size Status

Given the early termination of site activation and study enrollment since 24Jun2022 per Sponsor's decision, the trial has been changed to a Phase 2 study with all the analyses being exploratory. Subjects who have provided written informed consent may complete Screening and be randomized if they meet all eligibility criteria at the discretion of the Sponsor or their representatives. With the enrollment of the last subject on 01Jun2022, the subject status of this study is as follows:

• Screened: 27 subjects

Screen failure: 7 subjectsRandomized: 20 subjects

• Treated: 20 subjects

A total of 20 subjects were randomized in a 1:1 ratio to receive either CMP-001 in combination with nivolumab (Arm A) or nivolumab monotherapy (Arm B) with 9 subjects in Arm A and 11 subjects in Arm B as of the early termination of the study enrollment.

D. Treatment Randomization

Subjects who complete Screening procedures and meet inclusion/exclusion criteria will be randomized in a 1:1 ratio to Arm A (CMP-001 in combination with nivolumab) or Arm B (nivolumab monotherapy) using an Interactive Web Response System (IWRS) and stratified by the following factors:

- TNM Stage AJCC Cancer Staging Manual Eighth Edition (M0/M1a/M1b versus M1c/M1d)
- Tumor PD-L1 expression (Tumor Proportion Score, TPS %: ≥ 5% versus < 5%)

Regeneron Pharmaceuticals Inc. / Protocol: CMP-001-011 IQVIA Biotech (Confidential) Project # SZA58924

During the Screening process, subject-specific values will be recorded for each of the 2 stratification variables. Based on the entered values, the subject will be assigned to a treatment group according to a preprogrammed randomization schedule, which is designed to balance the 2 treatment groups by each variable to the extent possible.

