Subjects will be assigned a unique Subject identification (ID) number by the IWRS at randomization. This number will be recorded on the subject's electronic case report from (eCRF) pages and used to identify the subject throughout the study. Once a subject number is assigned, it cannot be reassigned to any other subject.

E. Assessment Schedule

See Protocol Table 1 for the study schedule of assessments.

F. End of Study

As determined by the Sponsor, site activation and enrollment into the study were terminated officially on 24Jun2022 with the trial changed to be a Phase 2 exploratory study. Any subjects meeting the entry criteria and eligible to be dosed in the Screening phase or on active treatment will be allowed to continue on treatment up until the 2-year treatment cutoff per the current protocol.

The end of study is defined as 100 days of safety follow-up after the last dose of the study treatment for the last ongoing subject.

III. Protocol Objectives

Per Sponsor's decision, enrollment was terminated before reaching the sample size planned for the analyses as described in the Protocol. All analyses will be exploratory as a Phase 2 study only. The performance of the statistical analysis for the protocol objectives and endpoints is contingent on the availability of the data source. Detailed information will be provided in the corresponding sections to follow.

A. Primary

Phase 2 Primary Objective

• To determine confirmed objective response rate (ORR) for treatment with first-line CMP-001 in combination with nivolumab versus nivolumab monotherapy in subjects with unresectable or metastatic melanoma

B. Secondary

Regeneron Pharmaceuticals Inc. / Protocol: CMP-001-011 IQVIA Biotech (Confidential) Project # SZA58924

Phase 2 Secondary Objective

- To evaluate the safety and tolerability of first-line CMP-001 in combination with nivolumab versus nivolumab monotherapy in subjects with unresectable or metastatic melanoma
- To evaluate the efficacy of first-line CMP-001 in combination with nivolumab versus nivolumab monotherapy in subjects with unresectable or metastatic melanoma

C. Exploratory

IV. Study Endpoints

A. Primary

Phase 2 Primary Endpoints

• The primary endpoint is the ORR, defined as the proportion of subjects with a confirmed objective response of CR or PR based on Response Evaluation Criteria in Solid Tumors version 1.1 (RECIST v1.1) as determined by BICR.

B. Secondary

Phase 2 Secondary Endpoints

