- Start or stop date with missing both the month and day will not be imputed.
- Start date missing the day will be imputed as the 1st day of the month of the start date.
- Stop date missing the day will be imputed as the last date of the month of the stop date or the study first dose date, whichever comes earlier.

D. Multiple Study Centers

No adjustment for study center is planned. Data from all investigational sites will be pooled in the analyses.

E. Covariate Adjustment in Primary Analysis

No covariate adjustments are planned.

F. Sample Size Reassessment

Not applicable.

G. Ad-hoc Analysis

There will be an ad-hoc analysis planned with the trigger event being two disease assessments after the enrollment of the last subject. The ad-hoc analysis of the endpoints will follow the efficacy analysis methods described in Section 0 below as well as the safety analysis methods detailed in Section IX below for the exploratory Phase 2 study.

The following unblinded subject information, efficacy-related and safety-related data displays will be produced for the purpose of the ad-hoc analysis. Unless stated otherwise, these displays are summary tables that summarize data by treatment group:

- Subject information
 - Demographics
 - Baseline characteristics
 - Disposition

Regeneron Pharmaceuticals Inc. / Protocol: CMP-001-011 IQVIA Biotech (Confidential) Project # SZA58924

- Medical history
- Cancer history
- ECOG

Efficacy

- o ORR, DOR, TTR, PFS per RECIST v1.1 by BICR and Investigator
- o OS
- Selected subgroup analysis

Safety

- Study drug exposure: CMP-001 and nivolumab
- Prior and concomitant medications
- Prior and concomitant procedures
- o All TEAEs (SAE, AESI)
- Summary of clinical laboratory results
- Summary of ECG results

H. Test Sizes

Given Sponsor's decision to terminate the study enrollment early, any tested hypotheses will be exploratory in essence and tested against 2-sided alternatives, using procedures that provide an expected probability of Type I error (α) of 0.05.

I. Multiplicity

Provided that the study enrollment was terminated early per Sponsor's consideration and the trial has been changed to an exploratory Phase 2 study, the previous sequential gatekeeping strategy is not applicable here anymore, and there will be no control for multiplicity applied. Thus, any tests performed will simply be exploratory and interpreted as such.

J. Analysis Sets

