The confirmed ORR will be calculated as the number of subjects with a confirmed CR or PR divided by the number of subjects in the analysis population [ORR = (confirmed CR + confirmed PR)/number of subjects] in each treatment group for the ITT Analysis Set. 95% exact CIs will be calculated for the ORR using the Clopper-Pearson method for each of the 2 treatment arms. Besides, ORR per RECIST v1.1 by Investigator assessment will also be summarized.

Confirmed Best Overall Response (BOR). The BOR is defined as the best response designation for each subject based on RECIST v1.1 as determined by BICR, recorded between the date of randomization and the date of PD or the date of subsequent new anti-cancer therapy, whichever is earlier. Per RECIST v1.1, CR or PR must be confirmed by a confirmatory assessment performed at least 4 weeks after the initial response. In the case of stable disease (SD), measurements must have met the SD criteria once at least 6 weeks after the date of randomization. The number and percentage of subjects within each BOR category (confirmed CR,

Page 23 of 46

Regeneron Pharmaceuticals Inc. / Protocol: CMP-001-011 IQVIA Biotech (Confidential) Project # SZA58924

confirmed PR, SD, PD, or not evaluable) will be summarized by treatment arm for the ITT Analysis Set. Besides, BOR per RECIST v1.1 by Investigator assessment will also be summarized.

The best overall response (BOR) will be derived as below:

Subjects who discontinue due to death as a result of disease progression, or disease progression prior to having a post-baseline tumor assessment will be classified as having a best response of PD. Subjects who discontinue prior to having a post-baseline scan for other reasons will be counted as non-responders in the ITT analyses (i.e., these subjects will contribute to the denominator, but not the numerator). Overall response assessment evaluated after subsequent new anticancer therapy will not be considered for BOR calculation.

Duration of Response (DOR). Duration of response will be based on RECIST v1.1 as determined by BICR and calculated for confirmed responders in each treatment arm of the ITT Analysis Set. The DOR will be measured from the time at which criteria are first met for CR or PR, whichever is first recorded, until the first date when recurrence or PD is objectively documented (taking as reference for PD the smallest measurements recorded on study).

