Last contact date/last date patient known to be alive from Long-Term Follow-Up eCRF 100-Day Follow-Up eCRF	Use if patient status is reported to be alive. Do not use if patient status is not reported unknown
End of study	Not lost to follow up
Start/end dates from drug administration record	Non-missing dose. Doses of 0 are allowed
Dosing prophylaxis eCRF	Prophylaxis given marked as yes
End of treatment date(s) from the End of Treatment eCRFs	No condition
Tumor assessment (RECIST v1.1 or iRECIST) date	Evaluation is marked as done
Laboratory/PK collection dates	Sample collection marked as done
Vital signs date	At least 1 non-missing parameter value
Physical examination	Evaluation performed marked as yes
12-Lead ECG	Evaluation performed marked as yes
ECOG performance status date	Non-missing ECOG performance status
Start/end dates of adverse events	Non-missing verbatim term
Start/end dates of concomitant medications and procedures	Non-missing verbatim term

B. Primary Efficacy Analysis

Primary Efficacy Endpoint. The primary efficacy endpoint for the exploratory Phase 2 study is the confirmed ORR based on RECIST v1.1 as determined by BICR. ORR and the 95% exact CIs will be calculated using the Clopper-Pearson method for each of the 2 treatment arms in the ITT Analysis Set.

Regeneron Pharmaceuticals Inc. / Protocol: CMP-001-011 IQVIA Biotech (Confidential) Project # SZA58924

Given Sponsor's decision to terminate the study enrollment early, the previous sample size calculated to achieve the power and effect size desired at the confidence level specified will not be reached. Hence, the analysis will simply be exploratory and interpreted as such.

C. Secondary Efficacy Analyses

The secondary efficacy endpoints include DOR, PFS, OS, DCR, treatment effect in non-injected target lesions based on the RECIST v1.1 by Investigator assessment, iORR, iDOR, and iPFS. Post-progression disease assessments of tumor response based on iRECIST evaluated by Investigator assessment will be summarized in a similar way to the RECIST v1.1 assessment, and will include the calculation of iORR, iDOR, and iPFS by treatment arm using the ITT Analysis Set as described in the previous sections.

iORR: As assessed by Investigator assessment according to iRECIST for the ITT Analysis Set in each of the treatment arm, iORR will be summarized and analyzed in a similar fashion to that of the ORR per RECIST v1.1.

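### The SAP's primary objective compares ORR between arms, but its primary analysis reports each arm separately and specifies no between-arm estimate

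*SAP*

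**What the plan says.** SAP III.A states the primary objective as a comparison: "To determine confirmed objective response rate (ORR) for treatment with first-line CMP-001 in combination with nivolumab versus nivolumab monotherapy". SAP II.A still describes the trial as randomized and active-controlled.

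The analysis is not comparative. SAP VIII.A says "95% exact CIs will be calculated for the ORR using the Clopper-Pearson method for each of the 2 treatment arms", and VIII.B repeats it as the primary analysis: "ORR and the 95% exact CIs will be calculated using the Clopper-Pearson method for each of the 2 treatment arms in the ITT" Analysis Set.

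Protocol 9.6.1 planned three outputs for ORR:
- a test: "ORR will be analyzed using a 2-sided Cochran-Mantel-Haenszel test stratified by stage and PD-L1 expression to compare the 2 treatment arms";
- an estimate: "Associated odds ratio and 95% CI will also be calculated";
- Clopper-Pearson intervals in each arm.

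The SAP keeps only the third. Section I.B settles which document applies: "In case of any discrepancies, this SAP will govern the analysis of data from this study". The protocol's odds ratio therefore does not carry over by default.

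SAP II.C gives the final numbers, "with 9 subjects in Arm A and 11 subjects in Arm B as of the early termination of the study enrollment", and VI.E says "No covariate adjustments are planned".

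**The concern.** The objective asks how ORR differs between the arms, and the specified analysis does not answer that. The SAP explains why confirmatory inference was abandoned (enrollment stopped early, planned power not reached, no multiplicity control). It does not say that the test and odds ratio were removed, or how the comparison will now be made.

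Readers will compare the two rates anyway. They can subtract one from the other, but the SAP specifies no interval for the result, and judging by whether the per-arm intervals overlap can mislead. If an interval is added later, its method will be chosen with the results by arm in hand, and the limits depend on the method. This is a real possibility: SAP VI.G plans an unblinded ad-hoc analysis that includes ORR by arm after two disease assessments, and SAP I.B and VI.M leave the sponsor's analysis team unblinded.

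**Working it through.** **1. Is there a between-arm ORR estimate anywhere in the SAP?** The places where one could be:
- VIII.A and VIII.B: ORR and exact interval in each arm.
- VI.H: a two-sided 0.05 level for any hypothesis tested, with no ORR test named.
- VIII.C figures: a forest plot of ORR with intervals, with no difference or ratio named.
- VIII.C non-injected lesions: headed as a treatment effect, but summarized in each arm.
- VIII.D: subgroup forest plots, with no treatment contrast named.

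None specifies a difference, ratio or odds ratio for ORR.

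**2. The protocol's own figure.** Inputs from Protocol 9.1: 65% v 40%, two-sided alpha 0.05, power 80%, continuity-corrected Z-test with pooled variance. The pooled rate is 0.525.

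- Uncorrected: n = [1.960·√(2·0.525·0.475) + 0.842·√(0.65·0.35 + 0.40·0.60)]² / 0.25² = (1.384 + 0.575)² / 0.0625 ≈ 61.4, so 62 per arm.
- Corrected: (61.4/4)·[1 + √(1 + 4/(61.4·0.25))]² ≈ 69.2, so 70 per arm, or 140 in total.

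This matches the protocol; power at 70 per arm is 80.5%. With 9 v 11, power at the same rates is 19% (pooled Z), 9% (continuity-corrected) or 11% (Fisher exact). Dropping the formal test is therefore understandable.

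**3. What a between-arm estimate would look like.** The documents give no response counts. Assume 6/9 v 4/11, the counts nearest 65% and 40%.

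- SAP output: Arm A 67% (Clopper-Pearson 30% to 93%); Arm B 36% (11% to 69%).
- Difference: 0.667 - 0.364 = 0.303.
- Wilson limits: Arm A 0.354 to 0.879; Arm B 0.152 to 0.646.
- Newcombe lower limit: 0.303 - √[(0.667 - 0.354)² + (0.646 - 0.364)²] = -0.118.
- Newcombe upper limit: 0.303 + √[(0.879 - 0.667)² + (0.364 - 0.152)²] = 0.603.
- Miettinen-Nurminen: -0.144 to 0.646.

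Other assumed counts (Newcombe): 4/9 v 4/11 gives +8 points (-30 to 44); 7/9 v 4/11 gives +41 points (-2 to 68).

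**4. Why two per-arm intervals are not enough.** Assume 7/9 v 3/11. The Clopper-Pearson intervals overlap widely, 40% to 97% and 6% to 61%. Yet the interval for the difference excludes zero: +7 to +74 points (Newcombe), +5 to +78 (Miettinen-Nurminen).

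**5. Expected behaviour of the interval.** For each of the 10 × 12 possible outcomes with n = 9 and 11, compute the 95% CI. Weight its width, and whether it contains the true difference, by the binomial probabilities.

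| True ORR, A v B | Method | Mean width | Coverage |
|---|---|---|---|
| 65% v 40% | Newcombe | 0.709 | 93.6% |
| 65% v 40% | Miettinen-Nurminen | 0.770 | 93.3% |
| 40% v 40% | Newcombe | 0.719 | 95.0% |
| 40% v 40% | Miettinen-Nurminen | 0.785 | 94.7% |

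The Newcombe mean width for 70 v 70 at 65% v 40% is 0.310. At these rates the small sample makes the interval wide, while coverage stays close to nominal.

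**The case against.** The best defence is that this is an openly descriptive plan for a terminated study of 20 subjects. The SAP says that it may differ from the protocol, that all analyses are exploratory, and that planned power will not be reached. The endpoint is defined as a proportion, so side-by-side rates are a recognisable descriptive answer. No decision in the SAP now depends on the contrast, any reader can compute one from the counts, and an interval over 70 points wide settles nothing. For DCR, the SAP spells out Clopper-Pearson intervals only.

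Much of this stands. Per-arm description is legitimate, no figure in the documents is wrong, and the practical gain is modest. The value of naming a method now is also limited. In the 6/9 v 4/11 example the two methods differ by only 3 to 4 points at each limit. The SAP already records the last enrollment and the treatment split, and the documents do not show whether outcome data had been seen when it was written.

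What does not stand is the step from no test to no estimate. Low power argues against a significance claim; it does not argue against stating the difference and how uncertain it is. As for DCR, the SAP's secondary efficacy objective is also comparative, and Protocol 9.6.4 and the SAP both say DCR is handled like ORR.

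**Conclusion.** The concern holds. The comparative primary objective in SAP III.A has no matching estimate in VIII.B or elsewhere in the SAP, and the protocol's between-arm analysis was removed without replacement or comment. It should be corrected, although correcting it will not make the study conclusive: an interval for the difference would average about 71 to 78 points wide, depending on the method and true rates. The main limit remains 20 subjects instead of 140.

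The widths and coverages rest on 9 v 11 subjects and two pairs of true rates (the protocol's 65% v 40%, and 40% in both arms). All response counts are assumed. The mismatch itself depends on none of these figures.

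**What to change.** In SAP VIII.B, add the unstratified ORR difference (Arm A minus Arm B) with a two-sided 95% CI, naming one method, either Newcombe or Miettinen-Nurminen. Either will serve; in the two scenarios above Newcombe was slightly narrower, with coverage at least as close to nominal. Add the same row for DCR in VIII.C. Label both exploratory and make no significance claim. State that they replace the protocol's stratified test and odds ratio.

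The unstratified form agrees with VI.E and suits the numbers: 20 subjects over four strata (two factors with two levels each) is 5 per stratum on average. A hazard ratio for PFS or OS is optional at most.

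If the sponsor wants per-arm description only, the objective in III.A should be reworded as estimation of ORR in each arm. That would make the SAP consistent but would leave the comparison unanswered.

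The cost is one row in each of two existing tables, from counts already tabulated and with no new data. The downside is a very wide interval, which the report must present as inconclusive.
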